2.0 Goals

2.1 Primary

2.11 The primary safety endpoint will include: any episode of major bleeding including fatal bleeding. The following criteria will be used to confirm and categorize a bleeding episode:

- Major bleeding is defined as overt bleeding plus a hemoglobin decrease of ≥ 2 g/dL or transfusion of ≥ 2 units of packed red blood cells, or intracranial, intraspinal/epidural, intraocular, retroperitoneal, pericardial, intra-articular, intramuscular with compartment syndrome or fatal bleeding. Intracranial hemorrhage includes intracerebral (hemorrhagic stroke), subarachnoid, and subdural bleeds.
- Clinically relevant non-major bleeding is defined as overt bleeding not meeting the criteria for major bleeding but associated with medical intervention, an unscheduled contact with a member of the health care team, or temporary cessation of study treatment.
- Minor bleeding is defined as overt bleeding that did not meet criteria for major bleeding or clinically relevant non-major bleeding.

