7.0 Protocol Treatment

7.1 Treatment Schedule - Use actual weight (Kg)

Arm	Agent	Dose Level	Frequency	Route
A	Apixaban*	10 mg	Twice daily days 1-7	Oral
		5 mg	Twice daily days 8-180	
B	Dalteparin*	200 IU/kg/day	Once daily for days 1- 30	Subcutaneous Injection**
		150 IU/kg/day	Once daily for days 31-180	

*If a dose of apixaban or dalteparin is not taken at the scheduled time, the dose should be taken as soon as possible on the same day and the prescribed dosing schedule should be resumed. The dose should not be doubled to make up for missed doses.

** The dosage will be calculated on the patient's current weight in kilograms, rounded to the nearest whole kilogram. The syringe dose will be chosen based on the weight adjusted calculation based on the table 7.11. The patient will be taught by on site nursing staff how to administer the medication, and also how to "waste" from each syringe such that the appropriate weight adjusted

dose is delivered.

7.11

Month 1: 200 IU/kg SQ daily

Body Weight (kg)	Dalteparin Dose (IU) once daily
≤ 40	7,500
41-56	10,000
57-68	12,500
69-82	15,000
83-94	18,000
95-107	10,000 & 10,000 = 20,000
108-120	18,000 & 5,000 = 23,000
121-133	15,000 & 10,000 = 25,000
134-147	18,000 & 10,000 = 28,000
148-160	15,000 & 15,000 = 30,000
≥161	200 IU/kg SQ daily

Months 2-6: 150 IU/kg SQ daily

Body Weight (kg)	Dalteparin Dose (IU) once daily
≤ 40	5,000
41-57	7,500
58-77	10,000
78-92	12,500
93-110	15,000
111-130	18,000
131-141	10,000 & 10,000 = 20,000
142-160	18,000 & 5,000 = 23,000
≥161	150 IU/kg SQ daily

- 7.12 **Dalteparin therapy is weight based dosing.** Monthly weights should be performed and communicated with the study coordinator. For patients experiencing more than 10% weight loss or gain, the dose of dalteparin will be adjusted to current body weight. Round according to table 7.11.
- 7.13 Scheduled visits should include a standardized assessment of the signs and symptoms of recurrent thromboembolism, bleeding episodes, and adverse reactions. Patients should be instructed to report to the clinic immediately (or call 911/go to the Emergency Room) if they had any bleeding, or symptoms of recurrent deep-vein thrombosis, pulmonary embolism, or both. Written patient education materials will be provided to each patient outlining signs and symptoms to watch for regarding VTE recurrences (appendix IX). All suspected episodes of recurrent thrombosis should be investigated with the use of objective

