Outdated or remaining drug is to be destroyed on-site as per procedures in place at each institution.

15.19b Nursing guidelines

- Assess patient's concomitant medications including OTC, and herbal products. There are several drug to drug interactions that may interfere with the absorption of agent. Additionally, warn patient to avoid taking medication with any other anti-platelet agents (i.e. aspirin, NSAIDS, etc.)
- Warn patients of risk of bleeding, (including serious life- threatening internal bleeding). Instruct patients to report these to the study team
- Patients should discuss any procedures with the study team and/or any provider prior to proceeding, due to the risk of post procedure bleeding.
- Rarely patients may have nausea, treat symptomatically and monitor for effectiveness
- Rarely LFT's may be elevated. Follow any monitoring as recommended by the study protocol.

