Local: Pain at injection site ($\leq 12\%$), hematoma at injection site ($\leq 7\%$)

$<1\%$ (Limited to important or life-threatening):

Alopecia, anaphylactoid reaction, gastrointestinal hemorrhage, hemoptysis, hypersensitivity reaction (fever, pruritus, rash, injections site reaction, bullous eruption), postoperative wound bleeding, skin necrosis, subdural hematoma, thrombosis (associated with heparin-induced thrombocytopenia). Spinal or epidural hematomas can occur following neuraxial anesthesia or spinal puncture, resulting in paralysis.

- 15.29a **Drug procurement:** Pfizer will supply the drug to Biologics, Inc. Each participating ACCRU treating location will order the drug from Biologics, Inc. Fax the Drug Order Request Form (found in the forms packet) to:
Biologics, Inc.
Attn. Clinical Research Services
Fax: [REDACTED]

Each participating ACCRU treating location will be responsible for monitoring the supply of dalteparin and will use the Drug Order Request Form to order additional supplies as needed.

Outdated or remaining drug is to be destroyed on-site as per procedures in place at each institution.

15.29b Nursing guidelines:

- Instruct patients on self-injection technique.
- Warn patient of increased risk of bleeding, including life threatening hemorrhage. Patients should report excessive bruising and/or bleeding to the study team.
- Monitor LFT's and alert study team to changes in values.
- Instruct patients that they need to notify their provider prior to any procedures, as their risk for bleeding is significantly increased.

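### Only the dalteparin nursing guideline tells patients to report bruising, which could add reported events to the secondary bleeding composite in that arm alone (minor)

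*Combined protocol and SAP*

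**What the plan says.** Two short staff lists in the Drug Information section cover patient counselling.

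- Apixaban, 15.19b: "Warn patients of risk of bleeding, (including serious life- threatening internal bleeding). Instruct patients to report these to the study team". Bruising is not named.
- Dalteparin, 15.29b: after a warning of raised bleeding risk, "Patients should report excessive bruising and/or bleeding to the study team".

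Each list also has an item on procedures. For apixaban: "Patients should discuss any procedures with the study team and/or any provider prior to proceeding, due to the risk of post procedure bleeding". For dalteparin: "Instruct patients that they need to notify their provider prior to any procedures, as their risk for bleeding is significantly increased".

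An instruction that does not depend on arm stands in 7.13: "Patients should be instructed to report to the clinic immediately (or call 911/go to the Emergency Room) if they had any bleeding". It does not name bruising either.

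In 2.11, an overt bleed short of major counts as clinically relevant non-major if it is linked to any one of three things, one of which is "an unscheduled contact with a member of the health care team". That category joins major bleeding in the secondary safety composite of 2.22, analysed under 16.22 in the same way as the primary endpoint. Section 1.5 describes an open-label trial, with central blinded adjudication of major bleeding and deaths. It does not mention clinically relevant non-major bleeding.

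**The concern.** In an open-label trial whose outcome is bleeding, both arms should be told to report the same things. Here one arm receives a cue that the other does not.

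The cue matters because of how 2.11 is built. Suppose a bruise is judged to be overt bleeding but needs no intervention and no pause in study drug. Found at a planned visit, it is minor bleeding. Telephoned in between visits, it can be clinically relevant non-major bleeding. A prompt to call can thus change the class of an event, and not only the chance that it is noticed.

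The direction is fixed: any effect adds events on dalteparin and makes apixaban look better. At stake is how far a favourable result on the secondary safety composite can be trusted.

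**Working it through.** **Step 1: the reporting instructions side by side.**

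| Item | Apixaban | Dalteparin |
|---|---|---|
| Told to report bleeding (nursing list) | yes, 15.19b | yes, 15.29b |
| Told to report any bleeding at once (7.13) | yes | yes |
| Told to report excessive bruising | no | yes, 15.29b |
| Bruising question in booklet, baseline and every 30 days (4.0) | yes | yes |
| Bleeding assessment every 30 days, and by phone at end of treatment and 3 months later (4.0) | yes | yes |

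The difference that remains is the single cue on bruising.

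**Step 2: which endpoint can it reach?** Major bleeding (2.11) needs a haemoglobin fall, a transfusion, a critical site or a fatal outcome, and is adjudicated blind. A telephoned bruise does not meet that definition by itself. Clinically relevant non-major bleeding can be met by an overt bleed plus an unscheduled contact, with no blinded adjudication stated. The exposure is therefore the composite in 2.22.

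**Step 3: inputs for an illustration.**
- 150 patients per arm and one-sided 0.05 (16.1). 16.22 calls for an analysis similar to the primary one, so the same level is taken for the composite.
- Dalteparin rates: 6% major and 11-14% clinically relevant non-major (16.1). Adding them gives a composite of 6% + 11% = 17%, or 6% + 14% = 20%. This treats the two as separate patients.
- No true difference, so both arms start at the same rate.
- Effect of the cue: the documents give no figure. Assumed at 0.5, 1 or 2 percentage points on dalteparin, that is 0.75, 1.5 or 3 patients of 150.

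**Step 4: false-positive rate.** A pooled two-proportion z-test stands in for the Cox model. With base rate p, excess d and mean rate m = p + d/2:

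SE = √(2·m·(1 − m)/150), and P(apixaban declared better) ≈ Φ(d/SE − 1.645).

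For p = 0.17 and d = 0.02: m = 0.18, SE = √(2 × 0.18 × 0.82/150) = 0.0444, d/SE = 0.451, Φ(−1.194) = 0.116. Exact enumeration of the two binomials gives 0.115.

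| Excess on dalteparin | Share of the 11% | Exact, base 17% | Exact, base 20% |
|---|---|---|---|
| 0 | 0 | 5.0% | 5.0% |
| 0.5 points | 0.5/11 = 4.5% | 6.2% | 6.2% |
| 1 point | 1/11 = 9.1% | 7.8% | 7.6% |
| 2 points | 2/11 = 18% | 11.5% | 11.1% |

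**Step 5: cross-check on the hazard scale.** Take 10% more clinically relevant non-major events on dalteparin only (11% becomes 12.1%). Events = 150 × (0.17 + 0.181) = 52.65. Apparent HR = ln(0.83)/ln(0.819) = 0.933. Then Φ(√(52.65/4) × |ln 0.933| − 1.645) = 8.2%. The z-test at the same excess (1.1 points) gives 8.1%, so the stand-in is adequate.

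None of this touches the plan's sample-size figures, which concern major bleeding only.

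**The case against.** The strongest reply is that the cue either cannot matter or is already covered. If a bruise is not overt bleeding, reporting it creates no event under 2.11. If it is, 7.13 already tells both arms to report any bleeding at once, in more urgent terms than either nursing list. Both arms also answer the same bruising question every 30 days and have the same scheduled bleeding assessments. Bruising also has a drug-specific reason to appear in 15.29b, since 15.28 lists injection-site haematoma at up to 7%.

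Much of this stands, and it keeps the point small. It does not close the gap. Whether a bruise is overt bleeding is left to open-label sites, and a patient who is told to report bleeding may not think of a bruise unless it is named. Scheduled questions find bruises at planned times, while the definition turns on unplanned contact. The 7% figure (0.07 × 150, about 10 patients) also shows that the cue is given in an arm with bruises to report. A real excess of bruising on dalteparin would be a drug effect and not bias; only the part of the reporting that is due to the cue is at issue.

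A reader might infer more than the documents support:

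- *That bleeding ascertainment as a whole is biased, including the primary endpoint.* Both arms are told to report bleeding, and major bleeding rests on objective criteria with blinded adjudication.
- *That dalteparin patients are told the trial's hypothesis.* The phrase "as their risk for bleeding is significantly increased" is the reason given for notifying a provider before a procedure. It makes no comparison with apixaban, and 15.19b has a parallel item. The apixaban warning is also serious in tone.
- *That the false-positive rate could approach 30%.* An excess of 3 or 5 points at a 17% base does give about 16% or 29%. But it means 3/11 = 27% or 5/11 = 45% more clinically relevant non-major bleeding from one cue, and nothing in the documents supports that.

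**Conclusion.** The point holds as a minor one. The two nursing lists differ in one reporting cue, bruising, and the 7.13 instruction does not name bruising for either arm. Through the unscheduled-contact route in 2.11, the cue could add events to the secondary safety composite on dalteparin only, in apixaban's favour. The documents do not show that it would.

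If the cue added 0.5 to 2 percentage points, the one-sided false-positive rate for the composite would be about 6-12% instead of 5%. That range rests on no true difference, a 17% composite rate (a 20% rate gives nearly the same), 150 patients per arm, a z-test in place of the Cox model, and an assumed size for the cue.

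**What to change.** Put one identical reporting sentence in 15.19b and 15.29b, asking patients to report excessive bruising and/or bleeding to the study team. Keep the bleeding-risk warnings in both arms. Removing them, or dropping bruising from both lists, would also make the arms alike, but at the expense of safety counselling. Drug-specific items such as injection technique stay separate.

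The cost is a wording change in the nursing guidelines and any matching site training sheet, plus a few more minor bruising reports to log on apixaban. Sample size, analysis and treatment do not change.

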Based on the assumptions above, a sample size of 300 patients (150 per arm) would be required. We would accrue an additional maximum of 5% to account for ineligible patients and patients who withdraw from the study prior to receiving treatment. Hence the total maximum target accrual would be 315 (= 1.05 x 300) patients.

The anticipated accrual period (assuming 10 patients per month) would be 30 months or approximately 2.5 years. It is anticipated that the primary analysis can take place after the last accrued patient was followed for 6 months or when 11 major bleeds have been observed.

16.2 Primary Hypothesis:

We hypothesize that apixaban is associated with a significantly lower rate of major bleed compared to dalteparin in the treatment of patients with active cancer and confirmed acute deep-vein thrombosis (DVT) or pulmonary embolism (PE).

There are two changes made to the analysis plan as of Amendment 3. The original analysis plan was formulated by the previous study statistician. The following changes are proposed by the current study statistician for reasons explained below without knowledge of the outcome data. The changes and rationale for those changes are summarized below.

1. The incidence of major bleeding (or DVT) will be computed using the cumulative incidence function treating death without major bleeding (or without DVT) as the competing risk. Rationale: to prevent potential bias in the comparison due to the difference in mortality rates between the two arms.
2. Unstratified Cox models will be used in all analyses instead of stratified Cox models. Rationale: Based on data from previous studies which are used to design this trial, the incidence of major bleeding is extremely low. There will be substantial loss of power with the use of stratified Cox models which the study was not powered for. Since this is a randomized study and the randomization is stratified by cancer stage and risk, we expect minimal confounding effect from these variables.

16.21 Primary Safety Analysis:

All patients who received at least one dose of either apixaban or dalteparin will be included in the primary analysis. Patients will be analyzed according to the drug they received because this is a safety analysis rather than an efficacy analysis. The analysis of major bleeding events will primarily focus on those events which occurred during treatment or within 7 days of treatment discontinuation. Major bleeding events observed later will be described separately. Patients who did not have a bleeding event during the predefined time of treatment and follow-up period, who were lost to follow-up, or who withdrew informed consent before the end of the predefined study duration and who did not have a bleeding event will be censored at the appropriate time. The frequency of major bleeding events will be summarized separately by treatment arm. The cumulative incidence of major bleeding at 6 months from treatment initiation and its associated 95% confidence interval will be estimated separately by treatment arm using a cumulative incidence function, treating death without bleeding as a competing risk. A Cox proportional hazard model will be used to determine the point estimate for the HR (comparing apixaban to dalteparin) and the p-value for the comparison between the two arms. If the one-sided p-value is less than 0.05, then apixaban will be declared to have a lower major bleeding rate in this population

16.22 Secondary Safety Analysis:

A sensitivity analysis of the primary safety endpoint will be performed using the intent-to-treat population. Cox's proportional hazard model will be used to compare the major bleed events between the two. As before, a one-sided p-value will be used to determine whether apixaban has superior safety (i.e. smaller major bleed event rate than the control).

The secondary safety endpoint analysis will be on a treatment received basis. In this analysis, the composite endpoint of bleeding event defined as a major bleed or a clinically relevant non-major bleed will be used. For this analysis we will only include events that occurred during treatment or 7 days after treatment termination. A similar analysis as described for the primary safety analysis will be used. The impact of baseline covariates on the safety outcome will be explored by adjusting for them in the Cox models. The frequencies of the separate components contributing to the safety outcome will be described. Other safety outcomes include all deaths and other vascular events. AEs will be coded using the MedDRA Dictionary. Emergent adverse events will be defined as AEs occurring or worsening after randomization but not more than 7 days after study medication discontinuation. Events occurring during the 30 day follow up period will be described.

16.23 Secondary Efficacy Analysis:

For the secondary efficacy analysis, the time to the first event of the composite DVT/PE outcome will be analyzed using the same methods described above for the primary endpoint. The impact of baseline covariates (location of DVT, renal clearance, age, sex, mobility at randomization, pulmonary disease, and cardiac disease) on the efficacy outcome will be explored adjusting for them in the Cox models. Since this is a secondary endpoint, there is no adjustment for multiple comparisons. This analysis will be conducted at the one-sided type I error of 0.05.

The assumption of proportional hazards will be checked for all Cox models (including primary and secondary endpoints ~~and secondary analyses~~) using graphical methods as log(-log)-plots and plots of scaled Schoenfeld residuals.

16.3 Handling of Missing Data:

Monitoring and auditing procedures should be followed, in order to comply with GCP guidelines. Each center will be audited at regular intervals to ensure compliance with the protocol, GCP and legal aspects. This will include on-site checking of the CRF for completeness and clarity, cross-checking with source documents, and clarification of administrative matters.

16.4 Interim Analysis and Study Monitoring:

No formal interim analysis is planned. Risk-benefit will be evaluated by the Mayo Clinic Data Safety and Monitoring Board (DSMB), which will give regular recommendation to the executive committee. Early termination of accrual will be considered if there is evidence of a significant difference in major bleeding rates between the comparators. Access to interim tabular risk benefit data will be restricted.

16.5 Adverse Event Stopping Rule:

The stopping rule specified below is based on the knowledge available at study development. We do note that the Adverse Event Stopping Rule may be adjusted in the event of either (1) the study re-opening to accrual or (2) at any time during the conduct of the trial and in consideration of newly acquired information regarding the adverse event profile of the treatment(s) under investigation. The study team may choose to suspend

accrual because of unexpected adverse event profiles that have not crossed the specified rule below.

Accrual will be temporarily suspended to this study if at any time we observe events that the study team considers to be at least possibly related to study treatment (i.e., an adverse event with attribute specified as “possible,” “probable,” or “definite”) that satisfy the following:

- If 5 or more patients in the first 20 treated patients of either of the study arms (or 20% of all patients after 20 are accrued) experience a grade 4 or higher non-hematologic adverse event.

We note that we will review grade 4 and 5 adverse events deemed “unrelated” or “unlikely to be related” to verify their attribution and to monitor the emergence of a previously unrecognized treatment-related adverse event.

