2.2 Secondary

2.21 The secondary efficacy endpoint of this study will be VTE recurrence including DVT, PE, fatal PE, or arterial thromboembolism. The following criteria will be used to confirm and categorize a VTE recurrence:

- Suspected (recurrent) DVT: The original DVT must be confirmed by duplex ultrasonography, venography, CT, or MRI. A recurrent DVT must be distinguished from the original thrombus by comparing serial imaging modalities. In order to be classified as a recurrent event, there must be new filling defects evident on the second study not appreciated on the original images or an interval study clearly showing thrombus resolution.
- Suspected (recurrent) PE: The original PE must be confirmed by CT, MR, conventional pulmonary angiography, or VQ perfusion imaging. A recurrent PE must be distinguished from the original thrombus by comparing serial imaging modalities. In order to be classified as a recurrent event, there must be new filling defects evident on the second study not appreciated on the original images or an interval study clearly showing thrombus resolution.
- Fatal PE: PE based on objective diagnostic testing, autopsy, or death which

cannot be attributed to a documented cause and for which PE/DVT cannot be ruled out (unexplained death).

- Incidental VTE recurrence: Due to the nature of cancer surveillance related imaging, it is anticipated that recurrent venous thrombosis or thrombus propagation may be identified. In order to be classified as an event, the thrombus in question must be distinguished from the original thrombus by comparing serial imaging modalities. In order to be classified as a recurrent event, there must be new filling defects evident on the second study not appreciated on the original images or an interval study clearly showing thrombus resolution.
- Arterial thromboembolism: Myocardial infarction (MI), stroke, transient ischemic attack (TIA), or peripheral arterial embolism.

- 2.22 The secondary safety endpoint will include the combined endpoints of any episode of major bleeding including fatal bleeding or any episode of clinically relevant non-major bleeding.

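### Section 16.23 carries the safety analysis's drug-received, on-treatment methods over to the only efficacy endpoint, states no as-randomised VTE analysis, and uses a composite that does not match 2.21

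*Combined protocol and SAP*

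**What the plan says.** Section 2.21 names one efficacy endpoint, "VTE recurrence including DVT, PE, fatal PE, or arterial thromboembolism". Its fatal PE category includes unexplained death, and it also counts incidental recurrence.

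Section 16.23 specifies the analysis by cross-reference: "the time to the first event of the composite DVT/PE outcome will be analyzed using the same methods described above for the primary endpoint". It names no population, grouping, time origin or event window of its own. It tests at one-sided 0.05.

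The methods described above are those of 16.21: patients with at least one dose, a focus on events during treatment or within 7 days of stopping, and later events described separately. On grouping, 16.21 says: "Patients will be analyzed according to the drug they received because this is a safety analysis rather than an efficacy analysis". The time origin appears in "The cumulative incidence of major bleeding at 6 months from treatment initiation".

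Section 16.22 adds: "A sensitivity analysis of the primary safety endpoint will be performed using the intent-to-treat population". For the bleeding composite it restates both basis and window: "The secondary safety endpoint analysis will be on a treatment received basis", and "For this analysis we will only include events that occurred during treatment or 7 days after treatment termination". It also says: "Other safety outcomes include all deaths and other vascular events".

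Sections 16.1 and 16.2 describe the cumulative incidence of major bleeding or DVT. The competing risk is death not preceded by the bleed or the DVT.

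**The concern.** VTE recurrence against dalteparin is the other half of the risk-benefit reading of any bleeding advantage. The plan's own reason for grouping by drug received does not extend to it. Carrying the 16.21 methods over gives a formally tested efficacy comparison in which patients are not compared as randomised and which focuses on time on drug. If only the Cox model and the cumulative incidence function carry over, the population and window are undefined. Under either reading, two statisticians could follow 16.23 and report different hazard ratios.

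The trial is open-label and compares tablets with injections, so equal stopping in the two arms cannot be presumed. If stopping differs, recurrences more than 7 days after stopping fall outside the main comparison, and more of them in one arm.

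The composite is a second gap. Arterial events count in 2.21, are absent from the DVT/PE outcome of 16.23, and may be what 16.22 lists among safety outcomes as other vascular events. An analyst cannot tell which list governs.

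**Working it through.** **1. The definitions side by side.**

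| Item | Major bleeding (16.21) | Bleeding composite (16.22) | VTE (16.23) |
|---|---|---|---|
| Population | At least one dose | Treatment received | Not restated |
| Grouping | Drug received, because it is a safety analysis | Treatment received | Not restated |
| Window | Focus on treatment + 7 days | Treatment + 7 days only | Not restated |
| Intent-to-treat analysis | Yes, as sensitivity (16.22) | None stated | None stated |

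| Event | 2.21 | 16.23 | 16.1 and 16.2 |
|---|---|---|---|
| DVT | Yes | Yes | Yes |
| PE | Yes | Yes | Not named |
| Fatal PE, including unexplained death | Yes | Not named separately | Not named |
| Arterial thromboembolism | Yes | No | No |

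**2. The plan's own figures.** None is given for the efficacy endpoint. The bleeding design reproduces: 4(1.645 + 0.842)²/(ln 0.22)² = 10.8, so 11 events, and 150 × (0.06 + 0.014) = 11.1 expected events. Nothing below touches it.

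**3. How far the population and window could move the VTE hazard ratio.**

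Inputs from the documents:
- 150 per arm (16.1).
- 9% six-month VTE risk and 39% mortality, from the 6-month dalteparin row of the 16.1 table.
- 8.8% on placebo and 1.7% on apixaban in the extension trial (1.4). The ratio 8.8/1.7 = 5.2 serves as an upper case for the post-stop hazard, because those patients had already completed 6 to 12 months of anticoagulation.

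Assumptions not in the documents:
- Equal on-treatment VTE risk in both arms.
- 15% stop apixaban and 30% stop dalteparin, uniformly over 180 days.
- Post-stop hazard ×1, ×2 or ×5.2.
- Deaths independent of stopping, and censored in the Cox model.

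Hazards per day: VTE −ln(0.91)/180 = 0.000524; death −ln(0.61)/180 = 0.00275.

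The limiting Cox HR θ solves ∫[e_A − (e_A + e_D)·θR_A/(θR_A + R_D)]dt = 0. Here e is the event rate and R the number at risk in each arm, A for apixaban and D for dalteparin.

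| Post-stop hazard | As-randomised HR | Treatment + 7 days HR | Events outside window | Shift in SE |
|---|---|---|---|---|
| ×1 | 1.00 | 1.00 | 2.0 of 21.4 | 0 |
| ×2 | 0.94 | 0.99 | 3.9 of 23.4 | 0.13 |
| ×5.2 | 0.83 | 0.97 | 9.1 of 29.2 | 0.43 |

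The last row in full: expected events are 13.30 and 15.91, so SE = √(1/13.30 + 1/15.91) = 0.372, and |ln(0.828/0.972)|/0.372 = 0.43. The as-randomised HR is below 1 because more dalteparin patients spend time off study drug. The on-treatment HR is not exactly 1 because the 7-day tail is also at the raised hazard.

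Variants:
- No deaths, ×5.2: 0.82 versus 0.97, 12.5 of 37.7 events outside the window, shift 0.52 SE.
- Stopping reversed (30%/15%): 1.00/1.06/1.21 versus 1.00/1.01/1.03.
- Equal stopping (20%/20%): 1.00 throughout.

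**4. The competing-event wording, if taken literally.** With c the hazard of the competing event and h that of the endpoint, CIF = h/(h + c) × (1 − exp(−180(h + c))). If fatal-PE deaths are competing events, the 6-month incidence is 7.1%. If an assumed 2%, 5% or 10% of deaths count as endpoint events, it is 7.9%, 9.0% or 10.9%. The documents give no arterial event rate, so the effect of leaving out arterial events cannot be sized.

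**The case against.** A cross-reference is a form of specification, and 16.21 supplies a population, grouping, window and origin. The phrase could even be stretched to take in the intent-to-treat sensitivity analysis. It is a stretch, because 16.22 confines that analysis to the primary safety endpoint. So an as-randomised VTE analysis is at most implied. The documents do not rule one out.

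A reader might infer that the plan misclassifies fatal PE deaths as competing events. The text does not establish this. Fatal PE is a kind of PE, so the DVT/PE outcome naturally contains it. The operative wording in 16.21, carried over, becomes death without the efficacy event. The conflict needs a literal reading of a parenthesis in 16.1 and 16.2 that is probably shorthand. The clear mismatch is arterial thromboembolism.

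A reader might also infer that the on-treatment window would change the efficacy conclusion. The figures do not support that. The stopping rates are assumed, and the larger shift needs ×5.2. Stopping study drug need not mean no anticoagulant: section 8.1 allows other anticoagulation at the physician's judgment for patients stopped for low creatinine clearance, and leaves those with severe kidney injury to treatment by their physician. Such treatment would reduce the shift.

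Finally, the endpoint is secondary and not powered, and 16.21 says that later events are described separately. This bears on the weight of the point. It does not supply the missing analysis.

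**Conclusion.** The point stands as one that should be corrected. Read plainly, 16.23 puts the only efficacy endpoint on a drug-received, treatment plus 7 days basis that the plan justifies for safety alone. It states no as-randomised VTE analysis and uses an outcome narrower than 2.21. These are findings of text and rest on no assumed rate.

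The numerical consequence is illustrative. Under 15%/30% stopping the shift is 0 to 0.43 SE of the log HR, or up to 0.52 SE with no deaths. It is zero if stopping is equal or the post-stop hazard is unchanged, and smaller if patients who stop receive other anticoagulants. It would move the estimate more than the significance verdict. A reader might infer that the bleeding result or the sample size is weakened; neither is affected.

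**What to change.** (a) In 16.23, report VTE for all randomised patients by assigned arm, as first event within a fixed 6-month window, whether or not study drug continues. State the origin, and make the window cover the whole planned treatment period. Treatment may start up to 5 days after registration (6.14) and runs to treatment day 180 (7.1). A count of 180 days from randomisation could therefore cut off the last treatment days, while 180 + 5 = 185 days would not. Report the drug-received, treatment plus 7 days analysis beside it, since the as-randomised estimate includes time off drug.

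(b) Use one composite in 2.21, 16.1, 16.2 and 16.23, or report VTE including fatal PE separately from arterial events. Define the competing event as death not counted as an endpoint event.

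(c) Keep collecting VTE, bleeding and death to the end of that window for consenting randomised patients who stop treatment early or fall under 13.1 to 13.3. Sections 4.0 and 18.1 need aligning: the monthly forms are tied to treatment, patients stopped under 8.1 go to observation, and 13.3 ends data submission for cancels.

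The cost is wording plus some extra outcome contacts. The 5% allowance in 16.1 (315 − 300 = 15 patients) indicates the number who are ineligible or withdraw before treatment. The documents give no number for early stoppers or major violations. Sample size, primary analysis and treatment rules do not change.
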